### 12.5.2 Exploratory Analyses

Exploratory and/or data driven analyses will be identified as such and documented in the final Clinical Study Report.

### 12.5.3 Final Analysis

After the last study participant has completed Week 24 (and the subsequent 28 day follow up) the data will be analyzed and the primary clinical/statistical study report will be prepared.

## 12.6 Analysis of Safety

### 12.6.1 Incidence of Adverse events

All AEs will be coded using the Medical Dictionary for Regulatory Activities (MedDRA). AEs will be summarized according to the number of subjects experiencing specific events, reported by system organ class, high level group term, high level term and preferred term. AEs will also be presented by severity and relationship to treatment. All data will be listed.

### 12.6.2 Clinical Laboratory Parameters

Routine samples are being collected for assessment of clinical chemistry and hematology. Summary tables at each time point and by toxicity grade will be presented by dose level. All data will be listed.

### 12.6.3 Vital Signs

Vital signs are being assessed frequently across the duration of the study. Summary tables will be produced for each sign (temperature, heart rate, respiratory rate, systolic and diastolic blood pressure) and by toxicity grade. All data will be listed.

## 12.7 Analysis of Pharmacokinetics

As serum concentrations of IMM-124E are not expected, concentrations of IMM-124E antibodies will be collected and simple concentrations of IMM-124E will be summarized by treatment visit. Actual dosing and sampling times will be captured. Serum concentrations of at least the lower limit of quantitation will be used in the analysis.

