### 3.5 Rationale

A close interplay exists between the gut and liver. This is based on the evidence that more than 70% of the blood liver supply derives from the portal vein, the direct venous outflow of the intestine [Compare *et al.* 2012].

Disturbances in the homeostasis between bacteria- and host-derived signals at the epithelial level lead to a break in intestinal barrier function and may foster “bacterial translocation”, defined as the migration of bacteria or bacterial products from the intestinal lumen to mesenteric lymph nodes or other extraintestinal organs and sites. While the full repertoire of gut-derived microbial products that reach the liver in health and disease is yet to be explored, the levels of bacterial LPS are increased in the portal and/or systemic circulation in several types of chronic liver diseases, including NASH [Manco *et al.*, 2010]. Derangement of the gut flora, particularly small intestinal bacterial overgrowth, occurs in a large percentage (20-75%) of patients with chronic liver disease. It has been suggested that fatty diets promote gut microbiota changes and endotoxins produced by gram negative bacteria promote the development of NASH [Compare *et al.* 2012].

Hepatic steatosis is commonly associated with factors such as obesity and sub-clinical insulin resistance. Vulnerability to subsequent insults such as endogenous or exogenous toxins increases the production of pro-inflammatory cytokines. This further exacerbates insulin resistance, oxidative stress and organelle dysfunction within liver cells. In addition, circulating LPS has been found to trigger a molecular cascade which results in the release of pro-inflammatory cytokines. The latter eventually leads to hepatocyte death and the accumulation of inflammatory cells seen in NASH. In mice, LPS has also been associated in studies with increase in body weight and accumulated intrahepatic triglyceride [Manco *et al.* 2010].

Bovine colostrum contains increased concentrations of immunoglobulins (mainly IgG) compared with normal cow's milk, presented with other physically protective milk proteins. IgGs are not absorbed into the blood and act in the lumen against bacterial antigens or interact at the mucosal surface with dendritic cells that sample antigens from gut contents, influencing populations of T regulatory lymphocytes.

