## 4. OBJECTIVES AND ENDPOINTS

### 4.1 Objectives

The primary objectives of this study are to:

- Evaluate the safety and preliminary efficacy of two dose levels of IMM-124E in reducing liver fat evaluated on MRI compared with placebo in subjects with biopsy proven NASH.

The secondary objectives are to:

- Determine the pharmacokinetic profile of IMM-124E;
- Assess the impact of treatment with IMM-124E on markers of glucose metabolism and on serum lipid profile;
- Assess the impact of treatment on liver function over 24 weeks;
- Establish the recommended dose.

Exploratory objectives are to investigate the impact of treatment on potentially relevant immune and metabolic biomarkers associated with NASH.

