#### Secondary endpoints:

##### Pharmacokinetics:

- Serum concentration of IMM-124E bovine antibodies over time (if measurable) including, but not limited to, maximum observed concentration (Cmax), minimum observed concentration (Cmin) and area under the concentration-time curve (AUC), and, if feasible, elimination half-life (T1/2)

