### 7.3.8 Blood Samples for Pharmacokinetics

Serum concentrations of IMM-124E will be quantified, where possible, at Baseline (prior to taking study medication), W4, W12 and W24. The data and actual times of blood sample collection will be recorded in the 24 hour format. At least 2 aliquots of 1mL of serum will be collected and stored at  $\leq -70^{\circ}\text{C}$  at each time-point, prior to analysis.

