7.3 Secondary efficacy analyses

The following analyses of secondary efficacy will be performed on the FAS population. However, if the results for the primary efficacy analysis differ across populations, the ITT and PP populations may also be subject to secondary efficacy analysis. For the analyses detailed in this section and section 7.4, inferential statistical analysis will be performed on the same basis as for the primary endpoint. For those values that are recorded at 3 or more time-points, the baseline value will be included in the repeated measures analysis as a covariate. For analyses with only a baseline and final value, t-tests or Wilcoxon rank-sum tests will be performed depending on the distribution of the data. In addition to this, the mean change from baseline for all relevant variables will be assessed and presented.

Serum concentrations of IMM-214E bovine antibodies (including but not limited to: maximum and minimum observed concentration, area under the concentration-time curve, and (if feasible) elimination half-life) will be summarised and tabulated by visit and time point. Pharmacokinetic coefficients, including but not limited to, maximal and minimal concentration, area under the concentration curve and, if possible, elimination half-life will also be summarised and tabulated with change from Baseline by visit.

Body mass index (BMI), waist circumference and waist:hip ratio with change from Baseline will be summarised and tabulated by visit and treatment group.

HbA1c, glucose and homeostatic model assessment of insulin resistance (HOMA-IR) will be summarised and tabulated with change from Baseline by visit and treatment group.

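### Protocol 12.7 analyses only serum concentrations at or above the LLOQ, which overstates exposure whenever some samples are quantifiable and others are not

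*Protocol*

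**What the plan says.** The PK profile is a secondary objective in Protocol 4.1: "Determine the pharmacokinetic profile of IMM-124E". The matching endpoint in Protocol 4.2 is "Serum concentration of IMM-124E bovine antibodies over time (if measurable) including, but not limited to, maximum observed concentration", followed by minimum concentration, AUC and, where feasible, half-life.

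The protocol does not expect to find much. Its rationale (3.5) says that "IgGs are not absorbed into the blood and act in the lumen against bacterial antigens". Protocol 12.7 opens with "As serum concentrations of IMM-124E are not expected, concentrations of IMM-124E antibodies will be collected" and then sets the inclusion rule: "Serum concentrations of at least the lower limit of quantitation will be used in the analysis".

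Sampling is sparse. Protocol 7.3.8 says "Serum concentrations of IMM-124E will be quantified, where possible, at Baseline (prior to taking study medication), W4, W12 and W24", which is four samples per subject, the first before any dose.

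SAP 7.3 tabulates serum concentrations by visit and time point. In a separate sentence it says that the PK coefficients "will also be summarised and tabulated with change from Baseline by visit". It also promises the mean change from baseline for all relevant variables. It has no rule for results below the LLOQ. SAP 3.3 reports n with each continuous summary, bases percentages on valid observations, leaves missing data unimputed in the basic and interim analyses, and lists all data collected.

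**The concern.** The inclusion rule removes the observations that the protocol expects to see. What remains describes the level among samples in which antibody was found. It does not describe the level in the arm.

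A reader of the PK table will want to know whether bovine antibody reaches the circulation, how often, and whether this differs between 600 mg and 1200 mg three times daily. A mean over quantifiable samples answers none of these well. It has a floor at the LLOQ however little is absorbed, and when two arms differ mainly in how often antibody is detected, conditioning on detection hides much of the difference.

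There is a knock-on effect for change from Baseline. If a subject's pre-dose sample is below the LLOQ and is dropped, that subject has no change in concentration even when a later sample is quantifiable. Antibody absent before dosing and present afterwards is the informative pattern, and it would be lost from such a summary.

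**Working it through.** The documents give no PK figure to reproduce: no LLOQ, no expected concentration and no expected share below the limit. Protocol 3.4.5 says that the pharmacokinetics have not been established. The direction of the bias can be derived; its size can only be illustrated.

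**Direction.** If every value used is at least the LLOQ, then so are their minimum, median and mean. The mean of all samples is a weighted average of the mean above the LLOQ and the mean below it. The first is therefore larger than the overall mean whenever both groups are present.

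**Size, by assumption.** Take concentrations as lognormal with geometric SD g, let s = ln g, let q be the share below the LLOQ, and let z be the standard normal quantile of q. Then

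reported mean / true mean = Φ(s − z) / (1 − q).

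| q | z | g = 2 (s = 0.693) | g = 3 (s = 1.099) |
|---|---|---|---|
| 50% | 0 | 0.756 / 0.50 = 1.51 | 0.864 / 0.50 = 1.73 |
| 80% | 0.842 | 0.441 / 0.20 = 2.20 | 0.601 / 0.20 = 3.01 |
| 90% | 1.282 | 0.278 / 0.10 = 2.78 | 0.427 / 0.10 = 4.27 |

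The overstatement grows as more samples fall below the limit, which is the direction the protocol expects.

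**Dose difference, by assumption.** Set the LLOQ to 1 unit, g = 3, and 90% below the LLOQ at the lower dose.
- Lower dose: log-mean = −1.282 × 1.099 = −1.408. True mean = exp(−1.408 + 1.099²/2) = 0.447. Reported mean = 0.447 × 4.27 = 1.91.
- Higher dose, with true exposure doubled: log-mean = −1.408 + 0.693 = −0.715. Share below LLOQ = Φ(0.715 / 1.099) = 74%. True mean = 0.895. Reported mean = 0.895 × Φ(1.099 − 0.651) / 0.258 = 2.34.
- Reported ratio = 2.34 / 1.91 = 1.22, against a true ratio of 2. The proportions quantifiable, 10% and 26%, show the difference plainly.

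**All samples below the LLOQ.** The concentration summary then has n = 0 and no mean, so nothing is biased.

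**What a count would give.** With 40 subjects sampled in an arm at a visit (Protocol 5.2 plans at least 40 per arm), 0 of 40 quantifiable has an exact two-sided 95% upper limit of 1 − 0.025^(1/40) = 8.8%. For both active arms together, 0 of 80 gives 1 − 0.025^(1/80) = 4.5%.

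**The case against.** The sentence in 12.7 is terse. The endpoint is conditional on being measurable, quantification is to be done where possible, and nothing says that results below the LLOQ go unreported. On this view only a convention is missing. That is a fair account of the SAP, which is silent. It does not dispose of Protocol 12.7, which states what enters the analysis; neither document overrides it.

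A reader might infer that the plan could never show absence of absorption. The documents do not support this. SAP 3.3 reports n with each summary and lists all data, so counts can be reconstructed and an all-negative result would appear as n = 0. Nor would a better analysis prove non-absorption: it could show only that serum was below the LLOQ at the sampled visits.

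A reader might also infer that SAP 7.3 expressly promises change from Baseline in concentration. The phrase "will also be summarised and tabulated with change from Baseline by visit" belongs to the PK coefficients, and the PK table titles in SAP section 12 do not mention change from Baseline. The general promise of mean change for all relevant variables may cover concentrations, so that part of the point is conditional.

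The objection that simple substitution is no cure stands. In a lognormal example with log-SD 1.0 and 95% below the LLOQ, setting those values to zero gives 0.26 times the true mean, and setting them to half the LLOQ gives 1.75 times. For that reason the count should lead.

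Finally, PK is descriptive, and no primary test or stated decision rule uses it. This limits the importance of the point but not its correctness.

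**Conclusion.** The point holds in a conditional form. As written, Protocol 12.7 overstates serum exposure whenever an arm and visit contain both quantifiable and unquantifiable samples. There is no bias when all samples fall on the same side of the LLOQ.

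The direction needs no distributional assumption. The size does: 1.5 to 4.3 times the true mean, and a two-fold dose ratio reported as about 1.2, rest on a lognormal shape, a geometric SD of 2 to 3 (3 for the dose ratio) and the assumed shares below the LLOQ. None of these inputs is in the documents.

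Two consequences follow. No percentage quantifiable with all analysed samples as denominator is planned, although it is the most informative summary when little exposure is expected. Any change from Baseline in concentration would be undefined for subjects whose pre-dose sample is below the LLOQ. The rule should be changed, but the impact is low: the primary efficacy analysis is untouched.

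**What to change.** In Protocol 12.7 and SAP 7.3:

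- Delete the restriction to concentrations at or above the LLOQ.
- Make the main PK summary the number and percent of all analysed samples at or above the LLOQ, by arm (including placebo) and visit, with exact confidence limits. State the LLOQ in the table.
- Keep samples below the LLOQ in the concentration summary under one convention fixed in advance. One workable choice is to report the median, shown as <LLOQ where it falls there, and to give no mean when more than half the samples are below the limit.
- Say how change from Baseline is handled when the pre-dose sample is below the LLOQ, or drop it for concentrations and report how many subjects move from unquantifiable to quantifiable.
- State that a serum level below the LLOQ at the sampled visits is not proof of no absorption.

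The cost is protocol and SAP wording and one extra table, with no new data. Wherever samples are mixed, the reported exposure will be lower than under the present rule.

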## 12.8 Interim Analysis

An un-blinded efficacy and safety interim analysis is scheduled

The interim analysis will be conducted on all primary and secondary outcome unblinded data by a third party,

The interim analysis will be carried out when at least 22 eligible subjects complete the full 24 weeks of treatment and have verified baseline and 24 weeks MRI data.

The goals of the interim analysis are as follow:

1. Full efficacy analysis
2. Full safety analysis
3. Determining the best performing dose
4. To correct for sample size.

To account for multiple comparisons between the interim and final analyses, the critical alpha level for the interim analysis will be set at 0.0000147 while the critical alpha level for the final analysis will be set at 0.0499. These values are based on 25% of the study endpoints being available for the interim analysis and symmetric two-tailed tests being used within the O'Brien-Fleming spending function. The study will not be terminated for either success or failure. The purpose of this interim analysis will

be to verify, and if necessary re-calculate, the required study sample size and to potentially discontinue the worse performing dose arm.

The Interim-Analysis will be carried out by a third party so both sponsor and investigators would remain blinded to the allocation of subjects within the study groups.

## 13. GENERAL STUDY ADMINISTRATION

### 13.1 Ethical Aspects

#### 13.1.1 Local Regulations/Declaration of Helsinki

The investigator will ensure that this study is conducted in full conformance with the protocol, the “Declaration of Helsinki and its amendments, and with the requirements of national drug and data protection laws of the countries in which the research is conducted.

The investigator will also ensure that the basic principles of “Good Clinical Practice” as outlined in 21 Code of Federal Regulations (CFR) 312, subpart D, and 21 CFR Parts 50 and 56 are adhered to, together with USA CFRs regarding Investigational New Drugs (INDs) and any local guidelines or regulations.

#### 13.1.2 Informed Consent

It is the responsibility of the investigator to obtain written informed consent from each subject participating in this study or legally acceptable representative after adequate explanation of the aims, methods, objectives and potential hazards of the study, prior to undertaking any study related procedures. A legally acceptable representative is an individual or other body authorized under applicable law to consent, on behalf of a prospective subject, to the subject’s participation in the clinical study. The investigator must also explain to the subject that they are completely free to refuse to enter the study or to withdraw from it at any time for any reason.

A generic informed consent form template is provided in [Appendix B](#) for the investigator to prepare the informed consent document to be used at his or her site. The written informed consent document should be prepared in the language(s) of the potential subject population.

The investigator must utilize an IRB/IEC approved consent form for documenting written informed consent. The original signed informed consent form should be retained in accordance with institutional policy, and a copy of the signed consent form should be provided to the subject or legally acceptable representative.

#### 13.1.3 Institutional Review Boards/Ethics Committees

A copy of the protocol, proposed informed consent form, other written subject information, and any proposed advertising material must be submitted to the IRB/IEC for written approval. A copy of the written approval of the protocol and informed consent form must be received by Immuron before recruitment of subjects into the study and shipment of investigational product. Approval from the committee must be obtained before starting the study and should be documented in a letter to the investigator specifying the protocol number and version and the date on which the committee met and granted the approval.

Any modifications made to the protocol and/or informed consent form after receipt of IRB or IEC approval must also be submitted by the investigator to the committee in accordance with institutional procedures and regulatory requirements.

When no local review board exists, the investigator is expected to submit the protocol to a regional committee. If no regional committee exists, the Sponsor will assist the investigator in submitting the protocol to a central Ethics Review Committee.

#### 13.1.4 Conditions for Modifying the Protocol

Protocol modifications which could potentially adversely affect the safety of participating subjects or which alter the scope of the investigation, the scientific quality of the study, the experimental design, dosages, duration of therapy, assessment variables, the number of subjects treated or subject selection

criteria, may be made only after consultation between an appropriate representative of the Sponsor and the investigator.

Protocol modifications (amendments) must be prepared by a representative of the Sponsor and initially reviewed and approved by the responsible medical monitor, scientist and (when applicable) the statistician.

All protocol modifications must be submitted to the IEC/IRB and responsible regulatory authority in accordance with local requirements. Approval must be awaited before significant changes can be implemented i.e. if the risk benefit ratio is affected and/or the modification represents a change in basic trial definitions such as objectives, design, sample size or outcome measures.

In the event of an emergency, the investigator may institute any medical procedures deemed appropriate. However, all such procedures must be promptly reported to Immuron, the Immuron Medical Monitor and the IEC/IRB.

Administrative changes of the protocol are defined as minor corrections and/or clarifications that have no effect on the way the study is to be conducted or on the safety of the subjects. These administrative changes will be agreed upon by Immuron and the investigator, and will be documented in a memorandum. The investigator will then notify the IEC/IRB of such administrative changes.

#### 13.1.5 Conditions for Terminating the Study

The study may be prematurely terminated by the IEC/IRB or relevant regulatory authorities if the perception of the benefit/risk becomes unfavorable for continuation of the study.

Additionally, Immuron reserves the right to terminate the study at any time on the basis of new information regarding safety or efficacy, or if study progress is unsatisfactory, or for other valid administrative or commercial reasons.

Should this be necessary, the procedures will be arranged on an individual study basis after review and consultation by all parties. In terminating the study, Immuron and the investigator will ensure that adequate consideration is given to the protection of the subjects' interests. The Investigator should promptly inform the subjects and ensure appropriate therapy and follow-up, and inform the relevant regulatory authorities and the IRB/IEC. All delivered study materials must be collected and all CRFs completed to the extent possible.

### 13.2 Study Documentation, CRFs and Record Keeping

#### 13.2.1 Investigator Files/Retention of Documents

The investigator must maintain adequate and accurate records to enable the conduct of the study to be fully documented and the study data to be subsequently verified.

These documents should be classified into two separate categories:

- (1) Investigator Site File (ISF), and
- (2) Subject clinical source documents.

The ISF will contain the protocol/amendments, CRFs, query forms, IRB/IEC and governmental approval with correspondence, informed consent, drug records, staff curriculum vitae and authorization forms and other appropriate documents and correspondence.

Subject clinical source documents include subject hospital/clinic records, physician's and nurse's notes, appointment books, original laboratory reports, EKG, EEG, X-ray, pathology and special assessment reports, and consultant letters. All clinical study documents must be retained by the

Investigator until at least 2 years after the last approval of a marketing application in an International Conference on Harmonization (ICH) region (i.e. USA, Europe, or Japan) and until there are no pending or contemplated marketing applications in an ICH region; or if no application is filed or if the application is not approved for such indication, until 2 years after the investigation is discontinued and regulatory authorities have been notified. The investigator must notify Immuron prior to destroying any clinical study records.

Should the investigator wish to assign the study records to another party or move them to another location, Immuron must be notified in advance.

If the investigator cannot guarantee this archiving requirement at the study site for any or all of the documents, special arrangements must be made between the investigator and Immuron to store these in a sealed container(s) offsite so that they can be returned sealed to the investigator in case of a regulatory audit. Where source documents are required for the continued care of the subject, appropriate copies should be made for storage offsite.

